9.6. Data management

A data management plan will be created and will describe all functions, processes, and specifications for data collection, cleaning and validation. Concurrent manual data review will be performed based on parameters dictated by the plan.

Paper-based CRF will be used to collect the data from the sites. Refer to Annex 1 for sample CRF.

9.7. Data analysis

The data collected on the CRF (demographic and other baseline data) will be transferred into a clinical database.

For continuous data, number of non-missing records, mean, standard deviation, median, minimum, maximum and the two-sided 95% confidence interval (CI) of the mean will be presented. For categorical data, number of non-missing records and percentages will be presented.

Patients who do not return for follow-up will not be replaced and will be treated as censored. Missing data will be censored and no imputation will be performed.

Frequency of AE/SAEs among the study participants during the study period will be calculated if applicable.

Concomitant medications entered into the database will be coded using the World Health Organization Drug Reference. Medical history/current medical conditions and AEs will be coded using the Medical Dictionary for Regulatory Activities (MedDRA) terminology.

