This study focuses on timely detection and characterization of serious and non-serious adverse events (AEs) including important identified and potential risks and AEs of special interest observed with intravitreal Ozurdex[®] injection for the treatment of visual impairment due to diabetic macular edema (DME) in the Indian population during usual clinical practice.

Ozurdex[®] (dexamethasone intravitreal implant) is a corticosteroid indicated for the treatment of macular edema following branch retinal vein occlusion (BRVO) or central retinal vein occlusion (CRVO); non-infectious uveitis affecting the posterior segment of the eye; and DME. Ozurdex[®] is an intravitreal implant containing 0.7 mg (700 mcg) dexamethasone in the Novadur[®] solid polymer sustained-release drug delivery system¹.

Diabetic macular edema

Diabetic eye disease (retinopathy) can damage the small blood vessels of the eye. Fluid leaking from these blood vessels may cause the central part of the retina (the macula) to swell. This is called DME. Diabetic macular edema is the most common cause of vision loss in people who have diabetes². Diabetic macular edema affects 20% of patients with diabetic retinopathy³. Diabetic macular edema is characterized by capillary leakage, fluid accumulation, and macular thickening following breakdown of the blood retinal barrier⁴. Inflammation plays a significant role in DME pathogenesis because the breakdown of the blood retinal barrier involves expression of inflammatory factors⁵ including vascular endothelial growth factor (VEGF), intercellular adhesion molecule-1, interleukin-6, monocyte chemotactic protein-1, leukostasis⁶ and alterations in endothelial tight junction proteins⁷.

India is second to China in having the maximum number of diabetics⁸. The International Diabetes Federation projects the increase in number of people with diabetes in India from 65.1 million in 2013 to 109 million in 2035⁹. This significant proportion of diabetes in India indicates an increase in diabetic retinopathy or DME cases. One risk factor for the development of diabetic retinopathy is hypertension associated with diabetes. The increase of such cases is directly proportional to the duration of diabetes. Proliferative diabetic retinopathy was seen in patients with 11 years of diabetes. Severe diabetic retinopathies were observed in 100% of patients with 25 years of diabetes¹⁰.

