The objective of this PMS program is to evaluate the safety profile of Ozurdex[®] by actively identifying and evaluating the occurrence of AEs and serious adverse events (SAEs) for 1 year period in adult Indian patients (\geq 18 years of age) who will be receiving at least one intravitreal Ozurdex[®] injection for the treatment of visual impairment due to DME.

9. Research methods

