9.5. Study size

No formal sample size calculation is performed since this is an observational, prospective, noninterventional study without a comparison group and the goal is to evaluate the usual clinical practice experience with Ozurdex[®] in all the eligible patients. Approximately 250 patients are planned to be enrolled into the study from 20 sites across India based on the enrollment potential and is considered a representative sample.

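### Section 9.7 plans confidence intervals for means of continuous data but none for the AE/SAE percentages, which are the study's only outcome

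*Protocol*

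**What the plan says.** The objective in Section 8 is to evaluate safety "by actively identifying and evaluating the occurrence of AEs and serious adverse events (SAEs) for 1 year period in adult Indian patients". Section 9.9 adds that only safety data are to be evaluated and that no hypothesis will be tested.

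Section 9.7 assigns summaries by type of data:
- Continuous data: the usual descriptive statistics, including "median, minimum, maximum and the two-sided 95% confidence interval (CI) of the mean will be presented".
- Categorical data: "For categorical data, number of non-missing records and percentages will be presented".
- Safety events, in a separate paragraph: "Frequency of AE/SAEs among the study participants during the study period will be calculated if applicable". Section 9.9 repeats this in similarly conditional terms.

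The data analysis paragraph of the abstract (Section 4) repeats the continuous and categorical rules and does not mention event frequencies. No interval for an AE, SAE or ADR proportion or rate appears anywhere in the protocol.

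On study size, Section 9.5 states "No formal sample size calculation is performed since this is an observational, prospective, noninterventional study without a comparison group", and then "Approximately 250 patients are planned to be enrolled into the study from 20 sites across India based on the enrollment potential".

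**The concern.** The protocol says which summaries carry an interval, and its only outcome is not among them. The continuous variables it names (age, height and weight in Section 9.3) describe the patients but do not answer the study question. The AE/SAE frequencies do answer it, and they are planned as bare figures.

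This matters more than usual here because Section 9.5 offers no precision or detection target. In a single-arm study with no test and no sample size rationale, the interval around the event percentage is the natural statement of what the data can and cannot exclude. Section 12.1 sends the final report to the agency for expert committee evaluation. Without intervals, a small or zero percentage would arrive there with no indication of the risks it leaves open.

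**Working it through.** The protocol has no precision or power figure to reproduce. It gives a size of about 250 and says that no formal calculation was done. The check is therefore what the planned output would leave unsaid.

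**Inputs**
- n = 250 (Section 9.5).
- Two-sided 95% level, as Section 9.7 already uses for continuous means.
- Event counts: the protocol gives no expected rate, so 0 to 25 events are an assumed, illustrative range.
- Evaluable patients below 250: no loss rate is given. Section 9.7 censors patients who do not return, and Section 9.9 warns of extensive missing data. Values of 200, 150 and 125 are assumed.

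**Exact (Clopper-Pearson) interval for x events in n patients**

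Lower limit = Beta quantile at 0.025 with parameters (x, n − x + 1), or 0 if x = 0. Upper limit = Beta quantile at 0.975 with parameters (x + 1, n − x). For x = 0 the upper limit reduces to 1 − 0.025^(1/n).

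| Events in 250 | Planned output | Exact two-sided 95% CI |
|---|---|---|
| 0 | 0.0% | 0 to 1.46% |
| 1 | 0.4% | 0.01 to 2.21% |
| 2 | 0.8% | 0.10 to 2.86% |
| 5 | 2.0% | 0.65 to 4.61% |
| 10 | 4.0% | 1.93 to 7.23% |
| 25 | 10.0% | 6.58 to 14.41% |

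For zero events the one-sided 95% upper limit is 1 − 0.05^(1/250) = 1.19%, in line with the rule of three (3/250 = 1.2%).

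**Zero events with fewer evaluable patients (assumed)**

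| n | 1 − 0.025^(1/n) |
|---|---|
| 250 | 1.46% |
| 200 | 1.83% |
| 150 | 2.43% |
| 125 | 2.91% |

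**Chance of seeing at least one event, 1 − (1 − p)^250, with all 250 fully followed**
- p = 1%: 1 − 0.081 = 91.9%
- p = 0.5%: 1 − 0.286 = 71.4%
- p = 0.1%: 1 − 0.779 = 22.1%

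An event with a true risk of 0.5% would thus be missed altogether with probability 28.6%, and the planned table would show 0%.

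**The case against.** The strongest reply is that interval methods for AE percentages are commonly left to the SAP, which is not at hand and could add them. A protocol silent on intervals would deserve that benefit. This one is not silent: it names the summaries that get an interval and omits the event percentages. An SAP that added them would be extending a stated rule, and the protocol is the place to correct that rule.

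A second reply is that the continuous/categorical rule may cover only baseline data, because it follows a sentence that describes the CRF data as demographic and other baseline data. That reading is open. On it, event frequencies are governed only by the later sentence, which still provides no interval, so the result is the same.

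Third, the absence of hypothesis testing is no defence. An interval is estimation, and the protocol already plans intervals without tests.

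Fourth, no estimate is biased, and a reader given count and denominator can compute a simple binomial interval. This stands, and it limits the weight of the point.

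Some stronger inferences are tempting but not supported:
- **That rare serious events are the declared focus.** Section 7 says "This study focuses on timely detection and characterization of serious and non-serious adverse events (AEs". It covers both kinds of event and does not mention rarity.
- **That 250 patients give a 95% chance of seeing any event with a risk of 1.2% or more.** The arithmetic is right (95.1%), but only if all 250 are followed for the whole period and every event is captured. Sections 9.7 and 9.9 give reason to doubt that.
- **That the intervals on continuous means are an error.** They are harmless.
- **That the agency would read 0% as no risk.** Nothing in the protocol shows this.

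**Conclusion.** The point holds as a recommended improvement to reporting. Section 9.7 leaves the only outcome without a measure of uncertainty while providing one for variables that answer no study question. At the planned size, zero events leaves a true risk of up to 1.46% open (exact two-sided 95%) if all 250 treated patients are evaluable. With an assumed 200 to 125 evaluable, the limit is 1.83% to 2.91%.

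These limits reflect sampling error alone. They do not cover missed events, or events that cannot be classed as new or pre-existing because their dates are missing, which Section 9.9 acknowledges. Figures per person-time would need a further assumption, because the protocol gives no expected follow-up. For zero events the exact two-sided upper limit is 3.689 divided by the patient-years: 1.48 per 100 for an assumed 250 patient-years, and 2.95 per 100 for an assumed 125.

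A reader might infer that the event percentages themselves would be wrong. The missing intervals do not make them so. What is missing is the statement of what those percentages can exclude.

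**What to change.** In Section 9.7, with a matching line in the abstract, state that the number and percentage of treated patients with at least one AE, SAE and ADR will be presented with exact (Clopper-Pearson) two-sided 95% confidence intervals, including when the count is zero, and with the denominator shown. Stating the denominator matters because Section 11.1 collects events from consent onward, whether or not the injection has been given.

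If rates per person-time are also reported, give exact Poisson intervals. That needs an end-of-follow-up or last-contact date for each patient. None is among the variables listed in Sections 9.2 and 9.3, although the sample CRF is not shown and may contain one.

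If Section 9.5 is to state precision, make it conditional on follow-up: for example, zero events among 250 treated and fully followed patients would exclude a risk above about 1.5%, and the limit rises as fewer are followed.

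The intervals on continuous means may stay. The cost for the proportions is a few sentences and minor programming, with no change to visits or patient burden. The downside is that the reported safety profile will look less certain.

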9.8. Quality control

Site Qualification visits will be performed by a CRA from along with a representative from Allergan. During the site initiation visit, the CRA will provide face to face training on the conduct of the study to the participating physician. The CRA will remotely manage this study and the details on Remote Site Management will be described in study specific plans. The CRA will remotely closeout each site after the last patient's final follow-up assessment is completed and all CRF data has been entered and retrieved and all outstanding issues at the site have been resolved or addressed. In the case where a site is closed before completion of the study, the site will communicate to the Institutional Ethics Committee (IEC) of the same and the CRA will remotely close out the site but will maintain contact with the physician regarding the study status and in case follow-up information is required.

9.9. Limitations of the research methods

This is an observational study aimed to collect and evaluate only the safety data. There is no hypothesis testing in the study to evaluate any statistical significance. Frequency of AE/SAEs will be calculated as appropriate. This is a single arm study where no comparisons are possible to assess causality. Incident and pre-existing safety event may not be able to be differentiated if the date of occurrence is not available. Information from this study would supplement safety data already available and is part of the regulatory commitment. As there is no study mandated visits or procedures, missing data could be observed to a large extent.

9.10. Other aspects

9.10.1 Source documents

The physician should maintain source documents for each patient enrolled in the study. Source documents such as patient charts and doctors' notes will be kept as part of the patients' medical records. Patient files including medical records and signed patient ICFs must be available for review in the event the site is selected for monitoring, audits, or inspections and must be safely archived for at least 5 years after completion of the study.

9.10.2 File retention and archiving

The physician at the study sites will maintain a record of each enrolled patient. Physicians will be instructed on source documentation that must be available to substantiate patient identification, eligibility and participation, proper informed consent procedures, dates of data collection, adequate reporting and follow-up of AEs, concomitant medication, and drug administration.

10. Protection of human subjects

Intravitreal Ozurdex[®] injection is marketed for various other indications as mentioned in the Prescribing Information¹. There are no additional anticipated risks to the patients with this product.

The confidentiality of records, notifications, contact details, databases and any other information generated during the study that could reveal the identity of patients will be guaranteed, respecting the privacy and in compliance with country requirements. All information related to this study is considered confidential and remains as exclusive property of Allergan.

11. Management and reporting of adverse events/adverse reactions

11.1. Definitions

Adverse event

An AE is any untoward medical occurrence in a patient or clinical investigation subject administered a pharmaceutical product and that does not necessarily have a causal relationship with this treatment. An AE can therefore be any unfavorable and unintended sign (including an abnormal laboratory finding), symptom, or disease temporally associated with the use of a medicinal (investigational) product, whether or not considered related to the medicinal (investigational) product. This includes but is not limited to AEs which arise from:

- the use of a medicinal product within the terms of the marketing authorization;
- the use outside the terms of the marketing authorization, including overdose, off-label use, misuse, abuse and medication errors;
- occupational exposure.

Note: AEs must be collected once informed consent has been obtained, regardless of whether or not the subject has been administered study drug. Patients who do not receive the injection will be replaced.

Serious adverse event

An SAE is any AE occurring at any dose that results in any of the following outcomes: death, a life-threatening AE, inpatient hospitalization or prolongation of existing hospitalization, a persistent or significant disability/incapacity, or a congenital anomaly/birth defect. Important medical events that may not result in death, be life-threatening, or require hospitalization may be considered as SAE when, based upon appropriate medical judgment, they may jeopardize the patient and may require medical or surgical intervention to prevent one of the outcomes listed in this definition.

Allergan considers all cancer AEs as SAEs. In addition, an abortion (spontaneous or non-spontaneous) is also considered an SAE.

Pre-planned surgeries or procedures for pre-existing, known medical conditions for which a subject requires hospitalization is not reportable as an SAE.

Any pre-planned surgery or procedure should be clearly documented in the site source documents by the medically qualified investigator at the time of the subject's entry into the study. If it has not been documented at the time of the subject's entry into the study, then it should be documented as an SAE and reported to Allergan.

Adverse drug reaction

Regarding marketed medicinal products: a response to a drug which is noxious and unintended and which occurs at doses normally used in man for prophylaxis, diagnosis, or therapy of diseases or for modification of physiological function. All noxious and unintended responses to a medicinal product related to any dose should be considered ADRs.

Severity of AE

A clinical determination will be made of the intensity of an AE. The severity assessment for an AE must be completed using the following definitions as guidelines:

| Mild | Awareness of sign or symptom, but easily tolerated. |
|----------|---|
| Moderate | Discomfort enough to cause interference with usual activity |
| Severe | Incapacitating with inability to work or do usual activity. |

All AEs/SAEs/ADRs that occur during and/or after administration of the product during the follow-up period will be collected regardless of causal relationship to the product.

All AEs, SAEs and ADRs (serious or not) should be recorded on the study CRF. All AEs, SAEs and ADRs should be reported to Allergan global safety team at

Each participating investigator will be trained on the recording of AEs/SAEs/ADRs. The physician or site staff should instruct patients to report SAEs and reportable AEs from the time of enrollment through end of follow-up or early discontinuation from the study during this time period.

Reporting of the events:

Each patient interview will begin with simple open-ended questions and questions designed to collect information regarding specific outcomes of interest. If a patient is seen by a non-study physician, the study physician and/or trained site staff should make every effort to follow-up with the relevant concerned health care provider to obtain all information necessary for the accurate reporting of the event in a timely manner.

All AEs, SAEs and ADRs (serious or not) should be recorded on the study CRF. All events reported on the CRF by the study physician will be confirmed by medical record review and/or direct follow-up with the treating physician. In the event of a death, cause of death will be recorded.

Since this is a non-interventional study, the following types of events should be sent to Allergan global safety team: AEs, SAEs, non-serious ADRs, pregnancies and special situations (lack of effect, overdose, medication error, misuse, abuse, off-label use, use while breastfeeding or occupational exposure).

Pregnancy and all SAEs are to be sent **within 24 hours** of awareness of the event either directly from the site to patient safety operations (PSO) by emailing or faxing (primary ; back-up) within 24 hours of the receipt date (or as soon as possible, but no later than 24 hours for death or life-threatening reports) to PSO. The site should also inform in parallel. See below for reporting pregnancies.

Similarly, non-serious AEs, non-serious ADRs and special situations should be reported by the site **within 10 calendar days** of receipt to PSO.

To report the SAEs, non-serious AEs, non-serious ADRs and special situations, the site representative completes the SAE and Non-Serious ADR Form (GSE-SIMR-F-041) and sends directly to Allergan PSO along with the fax cover sheet by emailing

or faxing (primary ; back-up) within their reportable timeframe as discussed above.

To report the pregnancies, Allergan pregnancy data communication forms (pre-delivery GSE-SIMR-F-005; post-delivery GSE-SIMR-F-006) should be used to report in a similar manner. The site should also inform in parallel.

If additional information is required, PSO will make this request by emailing the site. The site representative should provide the requested follow-up information to the PSO in writing either by fax or via e-mail attachment. The site should also inform in parallel.

Site will promptly inform the governing IEC of the SAE as required by the IEC.

Being a post marketing surveillance study, the AE or SAE reporting to governing health authority will follow the regulations applicable for a marketed product that is, all cases involving serious unexpected adverse reactions shall be reported to the licensing authority by Allergan within 15 days of initial receipt of the information and other non-serious AEs will be reported through Periodic Safety Update Report that follows the prescribed periodicity.

12. Plans for disseminating and communicating study results

12.1. Study reports

| Reports | Reporting Period | Data Lock | Planned submission |
|----------------------------|------------------|-----------|--------------------|
| | | Point | date |
| End of one year from | DD Month YYYY - | DD Month | Q4 2017 |
| study initiation | DD Month YYYY | YYYY | |
| Final report submitted to | | | |
| agency for further subject | | | |
| expert committee | | | |
| evaluation. | | | |
| | | | |

Annex 1. List of stand-alone documents

| Number | Form number | Title |
|--------|----------------|--|
| | | |
| 1. | NA | Prescribing Information of Ozurdex [®] Intravitreal |
| | | Implant |
| 2. | NA | List of investigators/sites |
| 3. | NA | Sample Informed Consent Form and Patient |
| | | Information Form |
| 4. | NA | Sample CRF |
| 5. | GSE-SIMR-F-005 | Allergan pregnancy data communication form – |
| | | Pre-delivery (initial) information. |
| 6. | GSE-SIMR-F-006 | Allergan pregnancy data communication form – |
| | | Post-delivery (follow-up) information. |
| 7. | GSE-SIMR-F-041 | Sample PMS AE Form (serious adverse event and |
| | | non-serious adverse drug reaction form) |
| 8. | NA | Good Pharmacoepidemiology Practices (GPP) |
| 9. | NA | Declaration of Helsinki(DOH) |
